#### 2.9.2 **Intraocular pressure**

IOP absolute values and changes (pre-injection) from baseline by visit and changes from pre-dose to post-dose assessments within a visit will be descriptively summarized. Additionally, the number and percentage of patients with baseline IOP  $\geq 25$  mmHg will be presented by visit (pre-injection, post-injection assessment [if applicable]). Summaries will be presented separately for the study eye from baseline to EoT period.

All IOP data will be listed for all patients and baseline IOP values  $\geq 25$  mmHg will be flagged.

#### 2.9.3 **Vital signs**

Vital signs (sitting systolic blood pressure, sitting diastolic blood pressure, sitting pulse, weight) will be summarized by descriptive statistics, by visit, presenting absolute and change from baseline values. Analysis will be based on the patients in the Safety Set for the baseline to EoT period. Using the critical values outlined in [Table 2-4](#), a shift table will be produced to summarize the shift from baseline to any vital signs values that are abnormally low or high. All data, including data from unscheduled visits, will be considered when identifying abnormal values.

By-patient listings will be provided for all vital signs data and values outside the clinical normal ranges (see [Table 2-4](#)) will be flagged.

**Table 2-4 Vital signs critical values**

Variable	Type of abnormality	Criterion
Systolic blood pressure (mmHg)	High	Either $\geq 180$ absolute with an increase from baseline $\geq 20$ absolute
	Low	Either $\leq 90$ absolute with an decrease from baseline $\geq 20$ absolute
Diastolic blood pressure (mmHg)	High	Either $\geq 105$ absolute with an increase from baseline $\geq 15$ absolute

Variable	Type of abnormality	Criterion
	Low	Either $\leq 50$ absolute with an decrease from baseline $\geq 15$ absolute
Pulse rate (bpm)	High	Either $\geq 120$ absolute with an increase from baseline $\geq 15$ absolute
	Low	Either $\leq 50$ absolute with an decrease from baseline $\geq 15$ absolute

#### 2.9.4 Laboratory evaluation

HbA1c and lipid levels will be presented using standard international (SI) units. Laboratory data - observed values or changes from baseline values at each visit - will be summarized using descriptive statistics. Analysis will be based on the patients in the Safety Set for the baseline to EoT period.

Two sets of shift tables will be provided. First, using the laboratory defined normal ranges from the raw data, a shift table will be produced to summarize the shift from baseline to any laboratory values that are abnormally low or high. All data, including data from unscheduled visits, will be considered when identifying abnormal values.

Second, clinical critical values are defined in [Table 2-5](#). Baseline critical values are defined by the absolute values only. Using these critical values, a shift table will be produced to summarize the shift from baseline to any laboratory values that are abnormally low or high. All data, including data from unscheduled visits, will be considered when identifying abnormal values.

By-patient listings will be provided for all laboratory data. Values outside the clinical normal ranges will be flagged.

**Table 2-5 Critical values for laboratory values**

Variable	Type of abnormality	Critical values
Cholesterol	Out of normal range (low): female	2.38 mmol/l; 92 mg/dl
	Out of normal range (low): male	2.12 mmol/l; 82 mg/dl
	Out of normal range (high): female	6.06 mmol/l; 234 mg/dl
	Out of normal range (high): male	4.97 mmol/l; 192 mg/dl
	Pathologic value: female and male	6.22 mmol/l; 240 mg/dl
	Extremely pathologic value: female and male	9.07 mmol/l; 350 mg/dl
HDL-Cholesterol	Out of normal range (low)	1.04 mmol/l; 40 mg/dl
	Pathologic value (low)	0.91 mmol/l; 35 mg/dl
	Extremely pathologic value (low)	0.65 mmol/l; 25 mg/dl
LDL-Cholesterol	Out of normal range (high)	3.38 mmol/l; 130 mg/dl

Variable	Type of abnormality	Critical values
	Pathologic value (high)	4.94 mmol/l; 190 mg/dl
	Extremely pathologic value (high)	6.50 mmol/l; 250 mg/dl
Triglycerides	Out of normal range (high)	1.71 mmol/l; 150 mg/dl
	Pathologic value (high)	3.42 mmol/l; 300 mg/dl
	Extremely pathologic value (high)	5.13 mmol/l; 450 mg/dl
HbA1c	Out of normal range (high)	6.2%
	Pathologic value (high)	6.8%
	Extremely pathologic value (high)	14.6% (deviation alert above 12.1%)

## 2.10 Pharmacokinetic endpoints

Not applicable.

## 2.11 PD and PK/PD analyses

[figure not shown]
Not applicable.

[figure not shown]
## 2.12 Patient-reported outcomes

[figure not shown]
Not applicable.

[figure not shown]
## 2.13 Biomarkers

[figure not shown]
Not applicable.

[figure not shown]

## 2.15 Interim analysis

No interim analyses will be performed.

## 3 Sample size calculation

A sample size of 133 patients per treatment arm will have 90% power to establish non-inferiority at a margin of 4 letters for the 0.5 mg ranibizumab “at investigators discretion” dosing regimens in comparison to 0.5 mg ranibizumab PRN in the mean average change in BCVA based on a one-sided 0.025 significance level, assuming a treatment difference of 0 letters, a SD of 10 letters and an underlying normal distribution for an unstratified t-Test (nQuery Advisor 7.0).

The Phase III study (RESTORE) results in the FAS suggest a mean average change in BCVA of 6 letters with a SD of about 7-8 letters for ranibizumab. To account for some more variability related to the re-treatment concepts and subgroup treated with additional PRP laser in this study as compared to RESTORE, a SD of 10 letters is assumed. To account for some drop outs 150 patients will be randomized per treatment arm.

As outlined in the study protocol, section “Summary of protocol amendments” (study protocol version no.1 including Amendment 1); further recruitment of patients into this study was revised and reduced. New and relevant scientific evidence regarding treatment patterns with ranibizumab was published which did not justify continuing the trial with newly included

patients. Therefore recruitment was terminated at the time when 135 patients were enrolled into the study, resulting in a reduced sample size present for analysis.

As a consequence results are to be interpreted in a purely descriptive manner. With an estimate of about 120-150 patients to be enrolled by end of recruitment the expected power would be about 55-60% and will be evaluated accordingly.

## 4 Change to protocol specified analyses

No change from protocol specified analysis was made.

## 5 Appendix

### 5.1 Imputation rules

#### 5.1.1 Adverse Events date imputation

##### 5.1.1.1 AE start date imputation

The following table explains the notation used in the logic matrix. Please note that completely missing start dates will not be imputed.

	Day	Month	Year
Partial Adverse Event Start Date	Not used	MON	YYYY
Treatment Start Date	Not used	TRTM	TRTY

The following matrix explains the logic behind the imputation.

	MON MISSING	MON < TRTM	MON = TRTM	MON > TRTM
YYYY MISSING	( 1 ) No convention			
YYYY < TRTY	( 2.a ) Before Treatment Start	( 2.b ) Before Treatment Start	( 2.b ) Before Treatment Start	( 2.b ) Before Treatment Start
YYYY = TRTY	( 4.a ) Uncertain	( 4.b ) Before Treatment Start	( 4.c ) Uncertain	( 4.c ) After Treatment Start
YYYY > TRTY	( 3.a ) After Treatment Start	( 3.b ) After Treatment Start	( 3.b ) After Treatment Start	( 3.b ) After Treatment Start

Before imputing AE start date, find the AE start reference date.

- If the (imputed) AE end date is complete and the (imputed) AE end date < investigational study treatment start date then AE start reference date = min(informed consent date, earliest visit date).
- Else AE start reference date = investigational study treatment start date

Impute AE start date:

1. If the AE start date year value is missing, the date uncertainty is too high to impute a rational date. Therefore, if the AE year value is missing, the imputed AE start date is set to NULL.
2. If the AE start date year value is less than the treatment start date year value, the AE started before treatment. Therefore:
  - a. If AE month is missing, the imputed AE start date is set to the mid-year point (01JULYYYY).
  - b. Else if AE month is not missing, the imputed AE start date is set to the mid-month point (15MONYYYY).
3. If the AE start date year value is greater than the investigational study treatment start date year value, the AE started after treatment. Therefore:
  - a. If the AE month is missing, the imputed AE start date is set to the year start point (01JANYYYY).
  - b. Else if the AE month is not missing, the imputed AE start date is set to the later of (month start point (01MONYYYY), AE start reference date + 1 day).
4. If the AE start date year value is equal to the investigational study treatment start date year value:
  - a. And the AE month is missing the imputed AE start date is set to the AE reference start date + 1 day.
  - b. Else if the AE month is less than the investigational study treatment start month, the imputed AE start date is set to the mid-month point (15MONYYYY).
  - c. Else if the AE month is equal to the investigational study treatment start date month or greater than the treatment start date month, the imputed AE start date is set to the later of (month start point (01MONYYYY), AE start reference date + 1 day).

If complete (imputed) AE end date is available and the imputed AE start date is greater than the (imputed) AE end date, then imputed AE start date should be set to the (imputed) AE end date.

### **5.1.1.2 AE end date imputation**

For the purpose of date imputation the treatment follow up period date is defined as the last available visit date, i.e. including unscheduled visits after the end of study visit.

1. If the AE end date month is missing, the imputed end date should be set to the earliest of the (treatment follow up period date, 31DECYYYY, date of death).
2. If the AE end date day is missing, the imputed end date should be set to the earliest of the (treatment follow up period date, last day of the month, date of death).
3. If AE year is missing or AE is ongoing, the end date will not be imputed.
4. If the imputed AE end date is less than the existing AE start date then use AE start date as AE end date.

## 5.1.2 Concomitant medication date imputation

### 5.1.2.1 CM start date imputation

The following table explains the notation used in the logic matrix. Please note that completely missing start dates will not be imputed.

	Day	Month	Year
Partial CM Start Date	Not used	MON	YYYY
Treatment Start Date	Not used	TRTM	TRTY

The following matrix explains the logic behind the imputation.

	MON MISSING	MON < TRTM	MON = TRTM	MON > TRTM
YYYY MISSING	( 1 ) Uncertain	( 1 ) Uncertain	( 1 ) Uncertain	( 1 ) Uncertain
YYYY < TRTY	( 2.a ) Before Treatment Start	( 2.b ) Before Treatment Start	( 2.b ) Before Treatment Start	( 2.b ) Before Treatment Start
YYYY = TRTY	( 4.a ) Uncertain	( 4.b ) Before Treatment Start	( 4.a ) Uncertain	( 4.c ) After Treatment Start
YYYY > TRTY	( 3.a ) After Treatment Start	( 3.b ) After Treatment Start	( 3.b ) After Treatment Start	( 3.b ) After Treatment Start

1. If the CM start date year value is missing, the imputed CM start date is set to one day prior to treatment start date.
2. If the CM start date year value is less than the investigational study treatment start date year value, the CM started before treatment. Therefore:
  - a. If the CM month is missing, the imputed CM start date is set to the mid –year point (01JULYYYY).
  - b. Else if the CM month is not missing, the imputed CM start date is set to the mid-month point (15MONYYYY).
3. If the CM start date year value is greater than the investigational study treatment start date year value, the CM started after treatment. Therefore:
  - a. If the CM month is missing, the imputed CM start date is set to the year start point (01JANYYYY).
  - b. Else if the CM month is not missing, the imputed CM start date is set to the month start point (01MONYYYY).
4. If the CM start date year value is equal to the investigational study treatment start date year value:
  - a. And the CM month is missing or the CM month is equal to the treatment start date month, then the imputed CM start date is set to one day prior to treatment start date.
  - b. Else if the CM month is less than the treatment start date month, the imputed CM start date is set to the mid-month point (15MONYYYY).
  - c. Else if the CM month is greater than the treatment start date month, the imputed CM start date is set to the month start point (01MONYYYY).

If complete (imputed) CM end date is available and the imputed CM start date is greater than the (imputed) CM end date, then imputed CM start date should be set to the (imputed) CM end date.

[figure not shown]
### **5.1.2.2 CM end date imputation**

[figure not shown]
1. If the CM end date year value is missing, the date uncertainty is too high to impute a rational date. Therefore, if the CM end year value is missing or ongoing, the imputed CM end date is set to NULL.
2. Else, if the CM end date month is missing, the imputed end date should be set to the earliest of the (treatment follow up period date, 31DECYYYY, date of death).
3. If the CM end date day is missing, the imputed end date should be set to the earliest of the (treatment follow up period date, last day of the month, date of death).
4. If the imputed CM end date is less than the existing CM start date, use the CM start date as the imputed CM end date.

### **5.1.3 Medical history date of diagnosis imputation**

Completely missing dates and partially missing end dates will not be imputed. Partial dates of diagnosis will be compared to the treatment start date.

- If year of diagnosis (or DIAG year) < investigational study treatment start date year
  - and DIAG month is missing, the imputed DIAG date is set to the mid-year point (01JULYYYY)
  - else if DIAG month is not missing, the imputed DIAG date is set to the mid-month point (15MONYYYY)
- If DIAG year = investigational study treatment start date year
  - and (DIAG month is missing OR DIAG month is equal to investigational study treatment start month), the imputed DIAG date is set to one day before investigational study treatment start date
  - else if DIAG month < investigational study treatment start month, the imputed DIAG date is set to the midmonth point (15MON YYYY)
  - else if DIAG month > investigational study treatment start month → data error
- If DIAG year > investigational study treatment start date year → data error

## 5.2 Efficacy variables and populations for analysis

Table 5-3 describes and summarizes the efficacy variables of the study eye, and the populations for the planned analyses.

**Table 5-3 Efficacy variables of the study eye**

		Analysis		
Efficacy assessment	Variable	Method	Population	Time Period
Primary efficacy				
BCVA	Visit-averaged change from baseline in BCVA	ANCOVA 	FAS (LOCF)	Baseline – EoT
		ANCOVA 	PPS (LOCF)	Baseline – EoT
		ANCOVA 	FAS (as observed)	Baseline – EoT
		ANCOVA 	FAS (LOCF)	Baseline – EoS
		MMRM 	FAS (LOCF)	Baseline – EoT
Secondary efficacy				
BCVA	BCVA change from baseline to month 12	ANCOVA 	FAS (LOCF)	Baseline - EoT
	BCVA change from baseline to month 12	ANCOVA 	FAS (LOCF)	Baseline - EoT
CSRT	CSRT change from baseline to month 12	ANCOVA 	FAS (LOCF)	Baseline - EoT
FCP thickness	FCP thickness change from baseline to month 12	ANCOVA 	FAS (LOCF)	Baseline - EoT

 The model includes the respective baseline variable as a linear covariate and the following categorical variables: treatment, center

 The model includes the respective baseline variable, relevant changes of HbA1c, blood pressure (systolic, diastolic), and lipid levels (cholesterol, HDL-cholesterol, LDL-cholesterol, triglycerides) as linear covariates and the following categorical variables: treatment, center

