9.5 Analysis of secondary and other variables

9.5.1 Efficacy variables

The analysis of the secondary efficacy objectives will focus on the study eye only and it will be based on the FAS.

At all the time points assessed, each efficacy variable will be presented graphically (where appropriate) and descriptive statistics provided based on absolute values and changes from baseline.

Of note is that for patients randomized to the DI, no monthly visit and consequently no monthly reporting schedule exists. Therefore efficacy data collected by visit will be described on a bi-weekly schedule for the DI arm. Furthermore and in order to allow for a visualization of data of both arms on a monthly basis, data collected in between two monthly visits (e.g. at Month 5.5) will be reported at the following monthly visit.

For continuous and ordered categorical variables, changes from baseline will be compared between treatment groups using ANCOVA models (with the baseline covariate)/ T-test. For treatment differences, 95% confidence intervals will be calculated for differences of means (based on ANCOVA models).

Secondary Efficacy variables

The variables related to the secondary objectives are described below:

1. Mean change from baseline in BCVA from baseline to month 12.
2. Number visits and injections, and treatment free intervals
3. Changes in central subfield retinal thickness (CSRT) and foveal center point thickness by SD-OCT.
4. Comparison of changes of 1,2 or more steps in DRS retinopathy scale between treatment arms compared to baseline
5. ANCOVA analysis of primary outcome with the additional covariates “relevant changes of HbA1c, blood pressure, lipid level”

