## 2.8.1 Secondary endpoints

The following secondary efficacy endpoints will be evaluated:

- Change of BCVA in ETDRS letters from baseline to month 12
- Number of visits, injections and TFIs
- Change of CSRT ( $\mu\text{m}$ ) from baseline to month 12
- Change in FCP thickness ( $\mu\text{m}$ ) from baseline to month 12
- Change in 0, 1, 2 or more steps in DRS from baseline to month 12
- ANCOVA analysis of primary outcome with the additional covariates: relevant changes of HbA1c, blood pressure (systolic, diastolic), and lipid levels (cholesterol, HDL-cholesterol, LDL-cholesterol, triglycerides)

Changes in CSRT and FCP thickness will be evaluated by the CRC assessing OCT images. Changes in DRS will be evaluated by the CRC scoring CF Photography and FA images and will be defined in 5 severity levels:

1. Mild non-proliferative retinopathy (NPDR)
2. Moderate NPDR
3. Severe NPDR
4. Proliferative DR
5. Status post panretinal laser coagulation - not gradable

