Additional ANCOVA models for the primary outcome (visit-averaged change from baseline in BCVA from month 1 to EoT) will be performed with the following extra binary covariates (Yes, No):

- relevant changes of HbA1c (defined as any change of HbA1c (%) from baseline of  $> 1\%$ )
- relevant changes of systolic blood pressure (defined as any change of systolic blood pressure (mmHg) from baseline  $> 30$ )
- relevant changes of diastolic blood pressure (defined as any change of diastolic blood pressure (mmHg) from baseline  $> 20$ )
- relevant changes of cholesterol (defined as any change in cholesterol from baseline of (1) for female:  $\leq 2.38$  mmol/l; 92 mg/dl or  $\geq 6.06$  mmol/l; 234 mg/dl, (2) for male:  $\leq 2.12$  mmol/l; 82 mg/dl or  $\geq 4.97$  mmol/l; 192 mg/dl)
- relevant changes of HDL-cholesterol (defined as any change in HDL-cholesterol from baseline of  $\leq 1.04$  mmol/l; 40 mg/dl)
- relevant changes of LDL-cholesterol (defined as any change in LDL-cholesterol from baseline of  $\geq 3.38$  mmol/l; 130 mg/dl)
- relevant changes of triglycerides (defined as any change in triglycerides from baseline of  $\geq 1.71$  mmol/l; 150 mg/dl)

For each ANCOVA model, the LS (“adjusted”) means for each treatment arm and estimates of the difference (DI - PRN) will be given along with the respective two-sided, 95% CI together with two-sided p-values. In order to derive the final ANCOVA model, the following steps will be used:

[figure not shown]
1. The importance of the individual dependent variables on the primary outcome response variable will be testing using the primary ANCOVA model (see [Section 2.6.2](#) for details) for FAS (LOCF). Inclusion in the primary ANCOVA model when  $p < 0.2$ .
2. The backward stepwise regression procedure will be used to choose the optimal set of dependent variables from the set of statistically significant dependent variables tested in step 1. The significance level to stay in the ANCOVA model is  $p < 0.05$ .

Note: In case of inadequate results, further modification of the model may be required.

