#### SAS code for ANCOVA analysis

ANCOVA model will contain ‘treatment’ and ‘center’ as categorical variables, and ‘baseline BCVA’ as continuous. For secondary analysis additional linear covariates might be included, such as ‘HbA1c’, ‘Blood pressure (systolic, diastolic)’, or ‘Lipid levels (cholesterol, HDL-cholesterol, LDL-cholesterol, triglycerides)’.

For the appropriate treatment difference, the treatment arms should be sorted or coded appropriately before using this model.

The ANCOVA analysis will be performed using SAS procedure PROC MIXED as below. Note that for this illustrative example:

- the data are stored in the file data\_set
- treatmentvar = treatment variable

- responsevar = dependent variable
- stratavar = stratification variable
- bsl = baseline value of the responsevar
- alpha = significance level (i.e. 0.05 produces two-sided 95% CI)
- control = control arm (Ranibizumab 0.5 mg in PRN treatment regime)

```
PROC MIXED DATA = <data_set>;
CLASS <stratavar> <treatmentvar>;
MODEL <responsevar> = <stratavar> <treatmentvar> <bsl>;
LSMEANS <treatmentvar> / PDIFF = all CL alpha = <alpha> OM;
RUN;
```

To get the one-sided p-value for the non-inferiority test (margin = 4): add -4 letters to control group and re-run the above code with alpha=0.025 and PDIFF=controlu('<control>').

To get the one-sided p-value for the superiority test (if applicable): re-run the above code with alpha=0.025 and PDIFF=controlu('<control>').

---

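### SAP Table 5-3 puts the HbA1c, blood-pressure and lipid ANCOVA on month-12 BCVA change, while the protocol and SAP 2.8 define it on the visit-averaged primary outcome; the covariate form is also ambiguous

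*SAP*

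**What the plan says.** The influence of HbA1c, blood-pressure and lipid changes is a named secondary objective in Protocol 2.1.2, where it is tied to the primary objective. Protocol 9.5.1 lists it as secondary variable 5: "ANCOVA analysis of primary outcome with the additional covariates". SAP 2.8.1 repeats this: "ANCOVA analysis of primary outcome with the additional covariates: relevant changes of HbA1c". SAP 2.8.2 is the most specific. The outcome is given as "Additional ANCOVA models for the primary outcome (visit-averaged change from baseline in BCVA from month 1 to EoT", and the models "will be performed with the following extra binary covariates (Yes, No". It then gives a cut-off for each of seven factors (HbA1c, systolic and diastolic pressure, total, HDL and LDL cholesterol, triglycerides), a screen at p < 0.2, and backward selection with p < 0.05 to stay.

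Table 5-3 in SAP 5.2 differs. Its only ANCOVA 2 row is for "BCVA change from baseline to month 12", in the FAS (LOCF), baseline to EoT. Footnote 2 describes that model as including "relevant changes of HbA1c, blood pressure (systolic, diastolic), and lipid levels (cholesterol, HDL-cholesterol, LDL-cholesterol, triglycerides) as linear covariates". The primary variable, "Visit-averaged change from baseline in BCVA", is a separate entry in the same table and has no ANCOVA 2 row. The ANCOVA code text in Section 5.2.1 says "For secondary analysis additional linear covariates might be included" and gives HbA1c, blood pressure and lipid levels as examples, without the qualifier about relevant changes. SAP Section 4 states that nothing was changed from the protocol's analysis.

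**The concern.** The same secondary analysis is attached to two different outcomes. The month-12 change is a separate secondary endpoint and reflects one time point; the visit-averaged change reflects the whole year. A factor that changes during the year may relate to one and not the other. Someone programming from Table 5-3 would report adjusted treatment differences, confidence intervals and p-values for an endpoint that the protocol did not attach to this objective. Someone programming from 2.8.2 would report the intended one.

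The covariate wording adds a second uncertainty. A slope on the raw change and a Yes/No threshold effect are different quantities and can rank the factors differently.

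**Working it through.** No sample-size or power figure is involved, so the main check is a comparison of texts.

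**Step 1: outcome.**

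| Place | Outcome of the systemic-factor model |
|---|---|
| Protocol 2.1.2 | primary objective |
| Protocol 9.5.1, item 5 | primary outcome |
| SAP 2.8.1 | primary outcome |
| SAP 2.8.2 | visit-averaged BCVA change, month 1 to EoT |
| SAP Table 5-3, ANCOVA 2 | BCVA change to month 12 |

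Protocol 9.4.1 and SAP 2.6.1 both define the primary variable as an average over post-baseline visits, so the last row cannot be read as another name for it. Four places agree and the table differs.

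**Step 2: covariate form.** Only SAP 2.8.2 says binary. Protocol 9.5.1 and SAP 2.8.1 speak of relevant changes and give no coding. Footnote 2 also speaks of relevant changes, which 2.8.2 defines as Yes/No, but calls them linear and sets them apart from the categorical terms. Two readings follow:

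- *Footnote 2 means the 0/1 indicators.* A 0/1 variable entered linearly contributes β for Yes and 0 for No, which is the same fit as a two-level class factor. The conflict is then wording only.
- *Section 5.2.1 means the raw values or changes.* The model is then different. HbA1c changes of +0.2, +0.9 and +1.1 points are three distinct values, but No, No, Yes under the 2.8.2 cut-off of more than 1%.

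One simulated data set illustrates this. Assumptions: 135 patients, 30 centers, no true treatment effect, standard-normal HbA1c change, visit-averaged outcome with mean 6 and SD 10 plus a slope of −1.5 per unit, month-12 outcome equal to that plus noise with mean 1 and SD 5, and an indicator for a change above 1 in either direction. The model was treatment + center + baseline BCVA + covariate.

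| Outcome | Covariate | Treatment difference (SE) | Covariate p |
|---|---|---|---|
| Visit-averaged | raw change | −0.8189 (1.8247) | 0.2113 |
| Visit-averaged | 0/1, linear | −0.8354 (1.8341) | 0.4701 |
| Visit-averaged | 0/1, class | −0.8354 (1.8341) | 0.4701 |
| Month 12 | raw change | −2.1782 (2.1449) | 0.3016 |
| Month 12 | 0/1, linear or class | −2.2022 (2.1422) | 0.2486 |

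Linear and class entry of the indicator coincide. The raw change gives a different covariate p-value, and the two outcomes give different treatment estimates. With no true effect simulated, the gap between −0.84 and −2.20 is chance; it shows only that the fits are not interchangeable. All p-values exceed 0.2, so no screening decision changes here, though one could in other data.

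**Step 3: selection.** Footnote 2 lists the factors and is silent on selection. SAP 2.8.2 specifies it, and Section 5.2.1 supplies separate backward-selection code (PROC GLMSELECT).

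**Step 4: can the table simply point to 2.8.2?** Not yet. The lipid cut-offs there are the out-of-normal-range limits of Table 2-5, which are absolute values, applied to changes from baseline (mmol/l):

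- HDL: Yes if the change is ≤ 1.04. A patient with no change has 0 ≤ 1.04, so Yes; only a rise above 1.04 gives No.
- Total cholesterol: Yes if the change is ≤ 2.38 or ≥ 6.06 (women), ≤ 2.12 or ≥ 4.97 (men). No change is again Yes.
- LDL: Yes only if the change is ≥ 3.38. A patient starting at the upper normal limit would have to reach 3.38 + 3.38 = 6.76, above the extremely pathologic limit of 6.50.
- Triglycerides: Yes if the change is ≥ 1.71. From the upper normal limit this means 1.71 + 1.71 = 3.42, exactly the pathologic limit.

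Taken literally, the HDL and total-cholesterol indicators would be Yes for nearly everyone and the LDL indicator No for nearly everyone. A near-constant covariate carries almost no information.

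**The case against.** The strongest defence is that Table 5-3 is a summary, with 2.8.2 as the operative text. The table is visibly incomplete: it has no rows for the PPS as-observed analysis, the completer analysis, the analysis excluding patients who stop treatment but stay in the study, the baseline-to-EoS analyses of month-12 BCVA and CSRT change, or the retinopathy scale, all of which the SAP text plans. This stands. A reader might infer that the specified analysis will not be run, but a missing row does not cancel an analysis that 2.8.2 sets out in full. The likeliest explanation is a mislabelled row.

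Three other stronger readings are tempting and also fail:

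- That the protocol and SAP 2.8.1 require binary covariates: only 2.8.2 does.
- That footnote 2 forces all seven factors in together, against the selection rule: it says nothing on selection, and the permissive wording in Section 5.2.1 is compatible with it.
- That the discrepancy opens a choice after results are seen: the SAP is written before unmasking, and analysis staff are masked until database lock. The plainer latitude is the note in 2.8.2 allowing further model modification if results are inadequate, which is a separate matter.

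What does not stand is that the summary status makes the row harmless. SAP 5.2 presents the table as describing the planned analyses, and no rule says that the text prevails over the table. A deliberate change of outcome would contradict Section 4.

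**Conclusion.** The outcome in the ANCOVA 2 row contradicts the protocol and the SAP's own Sections 2.8.1 and 2.8.2. This is firm and rests on the current text alone. The linear wording is an ambiguity: it is harmless if the 0/1 indicators are meant and a different model if raw values are meant, and the documents do not settle which.

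The size is small. One secondary analysis with seven candidate covariates is affected, in a trial whose analyses are all declared exploratory. The primary non-inferiority analysis does not use these covariates. No effect on the trial's actual results is shown; the simulated figures are illustrative. The statement that three of the four lipid indicators would be nearly constant assumes a literal reading of the cut-offs and that very large lipid rises are uncommon; the documents give no distribution of changes.

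**What to change.** 1. In Table 5-3, move the ANCOVA 2 row to the visit-averaged BCVA change, FAS (LOCF), baseline to EoT.
2. Reword footnote 2 and the ANCOVA code text in Section 5.2.1 to: binary (Yes/No) relevant-change indicators, selected by the steps in 2.8.2.
3. Before adding that cross-reference, correct the lipid definitions in 2.8.2. Each should be either a threshold on the change itself or a move across a stated absolute limit, with the direction given.
4. If a month-12 or continuous-covariate version is also wanted, list it as a separate supportive analysis and declare it in Section 4.

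Items 1, 2 and 4 are wording edits to the SAP. Item 3 needs a short decision on definitions. None needs new data or affects patients. All should be done before database lock.
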